3.4. Toxicities Observed in the Expansion Phase

Adverse events that meet the same grading criteria as the DLT criteria listed above will be discussed promptly by Pfizer and Investigators during the next available Safety meeting. At the meeting, the details of the toxicity will be presented, and actions to be taken (if any) will be discussed, which may involve individual participants, or the Expansion Cohort as a whole.

3.5. Recommended Part 2 Expansion Dose Definition

The RP2D is the dose chosen for further investigation based on Phase 1 study results. If the MTD proves to be clinically feasible for long-term administration in a reasonable number of participants, then this dose usually becomes the RP2D. Further experience with the MTD may result in a RP2D dose lower than the MTD.

The Expansion Dose recommended for Part 2 is: AdC68 6×10^{11} VP, 5 mg of pDNA, 80 mg of tremelimumab and 300 mg of sasanlimab.

4. PARTICIPANT ELIGIBILITY CRITERIA

This study can fulfill its objectives only if appropriate participants are enrolled. The following eligibility criteria are designed to select participants for whom participation in the study is considered appropriate. All relevant medical and nonmedical conditions should be taken into consideration when deciding whether a particular participant is suitable for this protocol.

4.1. Inclusion Criteria

Participant eligibility should be reviewed and documented by an appropriate member of the investigator's study team before participants are included in the study.

Participants, for each assigned part, must meet all of the following inclusion criteria to be eligible for enrollment in the study:

4.1.1. Part 1 Inclusion Criteria

1. Histological or cytological diagnosis of advanced NSCLC or metastatic TNBC (defined as HER2 negative by IHC, fluorescence in situ hybridization (FISH) or chromogenic in situ hybridization (CISH) and $\leq 10\%$ ER/PR stain positive by IHC) with progressive disease that is resistant to standard therapy or for which no standard therapy is available or is refused by the participant.
2. A mandatory archived formalinfixed paraffin embedded (FFPE) tumor tissue block (preferred) must be provided. If an FFPE tumor tissue block cannot be provided, sites should contact sponsor for approval to submit slides. For Part 1, if an archived FFPE tissue is not available, a de novo (ie, fresh) tumor sample can substitute and should be obtained in accordance with local institutional practice for tumor biopsies.
3. Females and/or male participants age ≥ 18 years.
4. Eastern Cooperative Oncology Group (ECOG) Performance Status (PS) 0 or 1.
5. Measurable disease as per RECIST v. 1.1.
6. Adequate Bone Marrow Function, including:
 - a. Absolute Neutrophil Count (ANC) $\geq 1,500/\text{mm}^3$ or $\geq 1.5 \times 10^9/\text{L}$;
 - b. Platelets $\geq 100,000/\text{mm}^3$ or $\geq 100 \times 10^9/\text{L}$;
 - c. Hemoglobin $\geq 9 \text{ g/dL}$.
7. Adequate Renal Function, including:
 - a. Estimated creatinine clearance $\geq 60 \text{ mL/min}$ as calculated using the method standard for the institution. In unequivocal cases, a 24 hour urine can be collected and used to estimate the creatinine clearance more accurately.
8. Adequate Liver Function, including:
 - a. Total serum bilirubin $\leq 1.5 \times \text{ULN}$ unless the participant has documented Gilbert syndrome;

- b. Aspartate and Alanine aminotransferase (AST and ALT) $\leq 2.5 \times$ ULN;
 $\leq 5.0 \times$ ULN if there is liver involvement by the tumor;
- c. Alkaline phosphatase $\leq 2.5 \times$ ULN ($\leq 5 \times$ ULN in case of bone metastasis).

9. Resolved acute effects of any prior therapy to baseline severity or National Cancer Institute (NCI) CTCAE V5.0 Grade ≤ 1 except for adverse events (AEs) not constituting a safety risk by investigator judgment.
10. Serum or urine pregnancy test (for females of childbearing potential) negative at screening.
11. Female participants of nonchildbearing potential must meet at least 1 of the following criteria:
 - Achieved postmenopausal status, defined as follows: cessation of regular menses for at least 12 consecutive months with no alternative pathological or physiological cause; status may be confirmed with a serum follicle-stimulating hormone (FSH) level confirming the postmenopausal state;
 - Have undergone a documented hysterectomy and/or bilateral oophorectomy;
 - Have medically confirmed ovarian failure.All other female participants (including female participants with tubal ligations) are considered to be of childbearing potential.
12. Evidence of a personally signed and dated informed consent document indicating that the participant [or a legally acceptable representative/parent(s)/legal guardian] has been informed of all pertinent aspects of the study].
13. Willing and able to comply with scheduled visits, treatment plan, laboratory tests, and other procedures.

4.1.2. Part 2 Inclusion Criteria

1. Histological or cytological diagnosis of locally advanced or metastatic NSCLC (squamous or non-squamous histology) meeting the following criteria:
 - a. Receipt of at least 1, but not more than 2, prior treatment regimens in the advanced disease setting. In addition to participants with established metastatic or recurrent disease, the advanced disease setting also includes participants with platinum-based adjuvant, neoadjuvant, or definitive chemoradiation therapy given for locally advanced disease followed by recurrent or metastatic disease within 6 months of completing therapy.

- b. Prior treatment must have included an anti-PD-1/PD-L1 and a platinum-based chemotherapy, which may have been given in combination, or sequentially;
 - c. Prior treatment must have included an appropriate TKI if activating mutations are present, eg, EGFR/ALK/ROS1/BRAF/RET/TRK;
 - d. Most recent treatment must have included anti-PD-1/PD-L1 for at least 4 months, without radiographic disease progression, followed by confirmed radiographic disease progression on or within 12 weeks of the last dose;
 - e. No more than 1 prior anti-PD-1/PD-L1 treatment regimen may have been given;
 - f. Prior anti-PD-1/PD-L1 may not have been discontinued permanently for toxicity.
 - g. No prior treatment may have been given with any immunologic therapy other than anti PD-1 or PD-L1.
2. A mandatory archived formalinfixed paraffin embedded (FFPE) tumor tissue block (preferred) must be provided. If an FFPE tumor tissue block cannot be provided, sites should contact sponsor for approval to submit slides. If an archived FFPE tissue is not available, a de novo (ie, fresh) tumor sample can substitute and should be obtained in accordance with local institutional practice for tumor biopsies.
3. Females and/or male participants age ≥ 18 years.
4. Eastern Cooperative Oncology Group (ECOG) Performance Status (PS) 0 or 1.
5. Measurable disease as per RECIST v. 1.1.
6. Adequate Bone Marrow Function, including:
 - a. Absolute Neutrophil Count (ANC) $\geq 1,500/\text{mm}^3$ or $\geq 1.5 \times 10^9/\text{L}$;
 - b. Platelets $\geq 100,000/\text{mm}^3$ or $\geq 100 \times 10^9/\text{L}$;
 - c. Hemoglobin $\geq 9 \text{ g/dL}$.
7. Adequate Renal Function, including:

4.2. Part 1 Exclusion Criteria

Participants, for each assigned part, with any of the following characteristics/conditions will not be included in the study:

4.2.1. Part 1 Exclusion Criteria

1. Participants with known symptomatic brain metastases, with the following two exceptions:

- a. Participants with previously diagnosed brain metastases are eligible if they have completed their treatment and have recovered from the acute effects of radiation therapy or surgery prior to study entry, have discontinued corticosteroid treatment for these metastases for at least 4 weeks and are neurologically stable for 3 months (confirmed by MRI)
- b. Participants with newly diagnosed brain metastases identified by a screening brain MRI who are clinically asymptomatic are eligible if the Investigator deems their clinical status acceptable for participation in the trial and all other inclusion and exclusion criteria are satisfied, including being neurologically stable for 3 months since the screening brain MRI. A baseline MRI at screening is to be conducted only if clinically indicated based on the treating Investigator's judgement

2. History of prior malignancy other than the disease under study within the past 3 years excluding successfully resected treated basal cell carcinoma or squamous cell carcinoma of the skin or adequately treated carcinoma in situ.
3. Participants with intolerance to or who have had (Grade ≥ 3) allergic or anaphylactic reaction to antibodies or infused therapeutic proteins.
4. Major surgery within 4 weeks prior to study entry.
5. Radiation therapy within 4 weeks prior to study entry.
6. Systemic anticancer therapy within 4 weeks prior to study entry.
7. Participant has AE(s) due to cancer therapeutics administered >4 weeks earlier, which have not recovered to CTCAE Grade ≤ 1 (except alopecia, and except for AEs not constituting a safety risk by investigator judgment).
8. Active and clinically significant bacterial, fungal, or viral infection, including hepatitis B virus (HBV), hepatitis C virus (HCV), known human immunodeficiency virus (HIV) or acquired immunodeficiency syndrome (AIDS)related illness.
HIV seropositive participants, who are healthy and low-risk for AIDS-related outcomes,¹⁴³ may qualify for inclusion in the study after discussion with the Sponsor.

The following criteria for immune status and HIV ongoing therapy must be met for a HIV seropositive participant to be eligible for the study:

- a. Immune status criteria:
 - CD4 $^{+}$ T-cell counts ≥ 350 cells/ μ L at the study start;
 - No history of AIDS-defining opportunistic infections;

- Only remote AIDS-defining opportunistic infections in the past and none in one year prior to study start.

b. Ongoing HIV therapy criteria:

- Must be receiving recommended concurrent ART treatment according to NIH guidelines;¹⁴⁴
- Began ART treatment >4 weeks prior to study start (to ensure ART is tolerated and toxicities are not confused with study drug toxicities);
- HIV viral load <400 copies/mL for >4 weeks prior to study start (to ensure ART is tolerated and HIV controlled).

Anti-retroviral medications should be listed as concomitant medication.

Equivocal cases of viral hepatitis may be eligible if they have a negative viral load.

9. Receipt of an immunosuppressive dose of corticosteroids (ie, 10 mg prednisone daily or equivalent) or other immunosuppressive medication (eg, methotrexate, rapamycin) within 2 weeks of registration. Note: Participants with adrenal insufficiency may take 5 mg of prednisone or equivalent daily. Topical applications, inhaled sprays, eye drops or local injections of corticosteroids are allowed. Low dose corticosteroids for a short duration [5 mg once daily (QD) prednisone for 2 weeks] as symptomatic treatment and upon with discussion with the sponsor is allowed.
10. History of or active autoimmune disorders (including but not limited to: myasthenia gravis, thyroiditis, pneumonitis, rheumatoid arthritis, multiple sclerosis, systemic lupus erythematosus, scleroderma) and other conditions that disorganize or alter the immune system. Active inflammatory gastrointestinal disease, Crohn's disease, ulcerative colitis, and primary sclerosing cholangitis are excluded, however, gastroesophageal reflux disease under treatment with protonpump inhibitors is allowed (assuming no drug interaction potential).
11. Acetylcholine receptor binding antibody ≥ 0.5 nmol/L.
12. Abnormal neurologic examination at screening indicating possible underlying autoimmune disorder(s).
13. Any of the following in the previous 12 months or currently: myocardial infarction, severe/unstable angina, coronary/peripheral artery bypass graft, symptomatic congestive heart failure, cerebrovascular accident, transient ischemic attack or symptomatic pulmonary embolism, as well as ongoing cardiac dysrhythmias of NCI CTCAE Grade ≥ 2 , atrial fibrillation or any grade, or QTc interval >470 msec at screening.

14. Individuals in whom a skin-fold measurement of the cutaneous and subcutaneous tissue for two or more eligible injection sites exceeds 50 millimeters (mm).
15. Bleeding diathesis or condition associated with prolonged bleeding time that would contraindicate IM injection.
16. Current use of any implanted electronic stimulation device, such as cardiac demand pacemakers, automatic implantable cardiac defibrillator, nerve stimulators, or deep brain stimulators.
17. Presence of any surgical or traumatic metal implants at the site of administration (medial deltoid muscles or overlying skin or vastus lateralis muscle).
18. Hypertension that cannot be controlled by medications (>150/100 mmHg despite optimal medical therapy).
19. Participation in other studies involving investigational drug(s) within 4 weeks prior to study entry.
20. Known or suspected hypersensitivity to any of the VBIR-2 components.
21. Other acute or chronic medical or psychiatric condition, including recent (within the past year) or active suicidal ideation or behavior or laboratory abnormality that may increase the risk associated with study participation or investigational product administration or may interfere with the interpretation of study results and, in the judgment of the investigator, would make the participant inappropriate for entry into this study.
22. COVID-19/SARS-CoV2: SARS-CoV2 testing is not mandated for entry into this protocol. However, testing should follow local clinical practice standards and requirements. A positive result on an approved test, even if the participant is asymptomatic, excludes a participant from this trial.
23. Investigator site staff members directly involved in the conduct of the study and their family members, site staff members otherwise supervised by the investigator, or participants who are Pfizer employees, including their family members, directly involved in the conduct of the study.
24. Fertile male participants and female participants of childbearing potential who are unwilling or unable to use 2 highly effective methods of contraception as outlined in this protocol for the duration of the study and for at least 5 months after the last dose of investigational product [*per Section 4.3 below*].

4.2.2. Part 2 Exclusion Criteria

Participants with any of the following characteristics/conditions will not be included in the study:

1. Participants with known symptomatic brain metastases, with the following 2 exceptions:
 - a. Previously Diagnosed Brain Metastases: Participants with previously diagnosed brain metastases are eligible if (a) they have completed their treatment and have recovered from the acute effects of radiation therapy or surgery prior to study entry, (b) have discontinued corticosteroid treatment for these metastases for at least 4 weeks and are neurologically stable for 3 months (confirmed by MRI).
 - b. Screening-Detected Brain Metastases: Participants with newly diagnosed brain metastases identified by a screening brain MRI who are clinically asymptomatic are eligible if (a) the Investigator deems their clinical status acceptable for participation in the trial and (b) all other inclusion and exclusion criteria are satisfied, including being neurologically stable for 3 months since the screening brain MRI. A baseline MRI at screening is to be conducted only if clinically indicated, based on the treating Investigator's judgement.
2. History of prior malignancy other than the disease under study within the past 3 years excluding successfully resected treated basal cell carcinoma or squamous cell carcinoma of the skin or adequately treated carcinoma in situ.
3. Participants with high-volume or visceral spread of disease, or those who are symptomatic from their disease, such that they are at risk for life threatening complications in the short term. Examples include participants with uncontrolled pleural, pericardial, or peritoneal effusions; pulmonary lymphangitis; and over 50% liver involvement. Note: Participants with indwelling catheter(s) for drainage, or requirement for intermittent drainage no more frequently than monthly, will be considered eligible.
4. Participants with intolerance to or who have had (Grade ≥ 3) allergic or anaphylactic reaction to antibodies or infused therapeutic proteins.
5. Major surgery within 4 weeks prior to first dose.
6. External beam radiation therapy to large areas of the thorax or other sites within 4 weeks prior to first dose; focal, palliative radiation within 2 weeks of first dose.
7. Systemic anticancer therapy within 2 weeks prior to first dose.
8. Participant has AE(s) due to cancer therapeutics administered >4 weeks earlier, which have not recovered to CTCAE Grade ≤ 1 (except alopecia, and except for AEs not constituting a safety risk by investigator judgment).

9. Active and clinically significant bacterial, fungal, or viral infection, including hepatitis B virus (HBV), hepatitis C virus (HCV), known human immunodeficiency virus (HIV) or acquired immunodeficiency syndrome (AIDS) related illness.

HIV seropositive participants, who are healthy and low-risk for AIDS-related outcomes,¹⁴³ may qualify for inclusion in the study after discussion with the Sponsor.

The following criteria for immune status and HIV ongoing therapy must be met for a HIV seropositive participant to be eligible for the study:

a. Immune status criteria:

- CD4⁺ T-cell counts ≥ 350 cells/ μ L at the study start;
- No history of AIDS-defining opportunistic infections;
- Only remote AIDS-defining opportunistic infections in the past and none in 1 year prior to study start.

b. Ongoing HIV therapy criteria:

- Must be receiving recommended concurrent ART treatment according to NIH guidelines;¹⁴⁴
- Began ART treatment >4 weeks prior to study start (to ensure ART is tolerated and toxicities are not confused with study drug toxicities);
- HIV viral load <400 copies/mL for >4 weeks prior to study start (to ensure ART is tolerated and HIV controlled).

Anti-retroviral medications should be listed as concomitant medication.

Equivocal cases of viral hepatitis may be eligible if they have a negative viral load.

10. Receipt of an immunosuppressive dose of corticosteroids (ie, 10 mg prednisone daily or equivalent) or other immunosuppressive medication (eg, methotrexate, rapamycin) within 2 weeks of registration. Note: Participants with adrenal insufficiency may take 5 mg of prednisone or equivalent daily. Topical applications, inhaled sprays, eye drops or local injections of corticosteroids are allowed. Low dose corticosteroids for a short duration [5 mg once daily (QD) prednisone for 2 weeks] as symptomatic treatment and upon with discussion with the sponsor is allowed.

11. History of or active autoimmune disorders (including but not limited to: myasthenia gravis, thyroiditis, pneumonitis, rheumatoid arthritis, multiple sclerosis, systemic lupus erythematosus, scleroderma) and other conditions that alter the immune system. Active inflammatory gastrointestinal disease, Crohn's disease, ulcerative colitis, and

primary sclerosing cholangitis are excluded; however, non-immune mediated gastroesophageal reflux disease (esophagitis/gastritis) under treatment with proton pump inhibitors is allowed (assuming no drug interaction potential).

12. Acetylcholine receptor binding antibody ≥ 0.5 nmol/L.
13. Abnormal neurologic examination at screening indicating possible underlying autoimmune disorder(s).
14. Any of the following in the previous 12 months or currently: myocardial infarction, severe/unstable angina, coronary/peripheral artery bypass graft, symptomatic congestive heart failure, cerebrovascular accident, transient ischemic attack or symptomatic pulmonary embolism, as well as ongoing cardiac dysrhythmias of NCI CTCAE Grade ≥ 2 , atrial fibrillation of any grade, or QTc interval > 470 msec at screening.
15. Cardiac Troponin-I (cTnI) must be measured and found to be within the normal reference range before the administration of the first dose. Abnormal circulating levels of cTnI are exclusionary.
16. Individuals in whom a skin-fold measurement of the cutaneous and subcutaneous tissue for 2 or more eligible injection sites exceeds 50 millimeters (mm).
17. Bleeding diathesis or condition associated with prolonged bleeding time that would contraindicate IM injection.
18. Current use of any implanted electronic stimulation device, such as cardiac demand pacemakers, automatic implantable cardiac defibrillator, nerve stimulators, or deep brain stimulators.
19. Presence of any surgical or traumatic metal implants at the site of administration (medial deltoid muscles or overlying skin or vastus lateralis muscle).
20. Hypertension that cannot be controlled by medications ($> 150/100$ mmHg despite optimal medical therapy).
25. Severely symptomatic Chronic Obstructive Pulmonary Disease (eg, requiring ambulatory oxygen).
21. Participation in other studies involving investigational drug(s) within 4 weeks prior to study entry.
22. Known or suspected hypersensitivity to any of the VBIR-2 components.
23. Other acute or chronic medical or psychiatric condition, including recent (within the past year) or active suicidal ideation or behavior or laboratory abnormality that may increase the risk associated with study participation or investigational product administration or may interfere with the interpretation of study results and, in the

judgment of the investigator, would make the participant inappropriate for entry into this study.

24. COVID-19/SARS-CoV2: SARS-CoV2 testing is not mandated for entry into this protocol. However, testing should follow local clinical practice standards and requirements. A positive result on an approved test, even if the participant is asymptomatic, excludes a participant from this trial.
25. Investigator site staff members directly involved in the conduct of the study and their family members, site staff members otherwise supervised by the investigator, or participants who are Pfizer employees, including their family members, directly involved in the conduct of the study.
26. Fertile male participants and female participants of childbearing potential who are unwilling or unable to use 2 highly effective methods of contraception as outlined in this protocol for the duration of the study and for at least 5 months after the last dose of investigational product [*per Section 4.3 below*].

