Cycle Day											Day 1	Day 29	Day 57	Day 85	Day 99		Every 3 Months	
Visit Window (Days)*			±1	±2	±2	±2	±4	±2	±4	±2	±2	±2	±2	±2	±4	±4	±10	

- Screening:** To be obtained within 28 days prior to study entry.
- Informed Consent:** Must be obtained prior to undergoing any study specific procedures. May be collected more than 28 days prior to study entry. As part of the consenting process, participants will be informed of the potential occurrence of immune related adverse events and will be provided with a Patient Information Card.

- Tumor History:** Will be collected within 28 days prior to study entry. Includes details of primary diagnosis and treatment history.

C
C
I

■

■

■

- Medical History:** Includes history of disease process other than NSCLC (active or resolved), smoking history, and significant concurrent illness. Includes prior treatments and any current medical treatment for any condition.
- Complete and abbreviated physical examinations:** A neurologic examination must be conducted at Screening to look for potential signs of underlying autoimmune disorders. In addition, all abbreviated physical examinations conducted during Cycle 1 must include a neurologic examination.
- Assessment of the Skin and Subcutaneous Tissue Thickness:** Assessment of the skin and subcutaneous tissue thickness at the eligible administration sites will be performed at screening as described in the TDS-IM Instructions for Use. The assessment procedure does not need to be repeated during the course of the study unless the participant experiences a greater than 10% change in body mass relative to screening.
- Vital signs:** Includes temperature, pulse, and blood pressure (BP) to be recorded in the seated position after approximately 5 minutes of rest. Vitals signs, including temperature, pulse, and BP to be recorded 1-hour post-study drug administration during each cycle on Days 1, 29, 57, and 85.

Protocol Activity	Screen ¹ (≤28 days)	Treatment Period										End of Treatment ³²	Post Treatment				Survival Follow-up ³⁴
		Cycle 1					Cycle 2						Follow- Up (Months after EOT visit)				
Study Day		Day 1	Day 8	Day 15	Day 22	Day 29	Day 43	Day 57	Day 71	Day 85	Day 113		Month 1 ³³	Month 2	Month 4	Month 6	Post 6-Month Follow-up
Cycle Day											Day 1	Day 29	Day 57	Day 85	Day 99		Every 3 Months
Visit Window (Days)*			±1	±2	±2	±2	±4	±2	±4	±2	±2	±2	±2	±2	±4	±10	

11. **Performance status:** Use Eastern Cooperative Oncology Group (ECOG) – see [Appendix 2](#).

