		Cycle 1					Cycle 2					End of Treatment ³²	Follow- Up (Months after EOT visit)				Survival Follow-up ³⁴	
Study Day		Day 1	Day 8	Day 15	Day 22	Day 29	Day 43	Day 57	Day 71	Day 85	Day 113						Post 6-Month Follow-up	
Cycle Day											Day 1	Day 29	Day 57	Day 85	Day 99	Every 3 Months		
Visit Window (Days)*		±1	±2	±2	±2	±4	±2	±4	±2	±2	±2	±2	±2	±2	±4	±4	±10	

21. **Registration:** Participant number and dose level allocation operated by Pfizer Inc.

22. **Investigational Product Administration:** Treatment to be administered after all other assessments required on that day have been performed.

23. **Tumor Assessments:** Tumor assessments will include all known or suspected disease sites. Screening images may be obtained within 5 weeks of registration. Imaging obtained as part of standard of care but within 28 days (-7 days) of registration may be used for screening assessment. Imaging may include chest, abdomen and pelvis CT or MRI scans, and bone scans. Bone scans will be performed at baseline if disease is suspected and on study as appropriate to follow disease. Baseline central nervous system (CNS) imaging MRI or CT Brain to be conducted only if clinically indicated based on the investigator's judgement. CT or MRI scans, as well as bone scans, when indicated, are to be done every 8 weeks (±5 days) with the first one to occur 8 weeks after C1D1 Repeat imaging will be completed every 8 weeks up to and including Month 8 (Week 32) or until disease progression that requires new treatment modality, permanent discontinuation, or death. Disease progression will be confirmed with 2 consecutive timepoints at least 4-8 weeks apart in the absence of rapid clinical deterioration. Tumor assessment should be repeated at the End of Treatment visit if more than 6 weeks have passed since the last evaluation.

CCI

25. **Acetylcholine receptor (AChR) antibody:** Sample to be sent to the central laboratory for analysis. CCI

The evaluation for AChR antibodies is included to exclude participants who test positive at screening as agreed upon with the United States Food and Drug Administration (US FDA) and to confirm requirement for evaluation if myasthenia gravis is suspected.⁹⁹

CCI

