3.1.2. Dose Expansion (Part 2)

The Expansion Phase will enroll participants in 1 cohort of participants with metastatic or locally-advanced NSCLC who have previously received treatment with a platinum-based chemotherapy regimen and not more than one treatment with an immune checkpoint inhibitor regimen either concurrently or sequentially with the chemotherapy.

Participants will participate in the active treatment period of the study for approximately 9 months. This includes a 28 day screening period followed by 2 cycles of vaccine treatment, totaling 8 months in duration. After completion of the active treatment phase (vaccine prime, pDNA boosts, checkpoint inhibitor support), participants will then enter the maintenance phase of the study (pDNA boosts only with checkpoint inhibitor support).

[figure not shown]
Treatment will continue until: disease progression, unacceptable toxicity, death or participant's or investigator's decision occurs. Since the treatment effect of cancer immunotherapy can often be delayed, participants will be encouraged to continue on study treatment for at least 24 weeks before an investigator considers removing the participant due to disease progression, as long as (a) Participant and investigator agree; (b) Participant continues to meet all other study protocol eligibility criteria; (c) Toxicity remains acceptable; and (d) No deterioration of participant performance status. Disease progression will be confirmed with 2 consecutive timepoints at least 4-8 weeks apart in the absence of rapid clinical deterioration.

Participants who demonstrate clinical benefit with manageable toxicity and who are willing to continue receiving study treatment will be given the opportunity to continue treatment upon agreement between the investigator and sponsor. When the participant discontinues treatment, they will then enter a 6 month post-dose follow-up period to assess safety CCI

The end of the study is the last participant last visit.

The overall design is presented in Figure 1 below:

Figure 1. Study Design

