All sites of disease must be assessed at baseline. Baseline assessments should be done as close as possible prior to study start. For an adequate baseline assessment, all required scans must be done within 28 days prior to treatment and all disease must be documented appropriately. If baseline assessment is inadequate, subsequent statuses generally should be indeterminate.

Target lesions

All measurable lesions up to a maximum of 2 lesions per organ, 5 lesions in total, representative of all involved organs, should be identified as target lesions at baseline. Target lesions should be selected on the basis of size (longest lesions) and suitability for accurate repeated measurements. Record the longest diameter for each lesion, except in the case of pathological lymph nodes for which the short axis should be recorded. The sum of the diameters (longest for non-nodal lesions, short axis for nodal lesions) for all target lesions at baseline will be the basis for comparison to assessments performed on study.

- If two target lesions coalesce the measurement of the coalesced mass is used. If a large target lesion splits, the sum of the parts is used.
- Measurements for target lesions that become small should continue to be recorded. If a target lesion becomes too small to measure, 0 mm should be recorded if the lesion is considered to have disappeared; otherwise a default value of 5 mm should be recorded.

NOTE: When nodal lesions decrease to <10 mm (normal), the actual measurement should still be recorded.

Non-target disease

All non-measurable disease is non-target. All measurable lesions not identified as target lesions are also included as non-target disease. Measurements are not required but rather assessments will be expressed as ABSENT, INDETERMINATE, PRESENT/NOT INCREASED, INCREASED. Multiple non-target lesions in one organ may be recorded as a single item on the case report form (eg, 'multiple enlarged pelvic lymph nodes' or 'multiple liver metastases').

OBJECTIVE RESPONSE STATUS AT EACH EVALUATION

Disease sites must be assessed using the same technique as baseline, including consistent administration of contrast and timing of scanning. If a change needs to be made the case must be discussed with the radiologist to determine if substitution is possible. If not, subsequent objective statuses are indeterminate.

Target disease

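### Part 2 exclusion 1b counts 3 months of stability from the screening brain MRI, which no documented screening window can contain, and its stem does not cover the people it admits

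*Protocol*

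**What the plan says.** Protocol section 4.2.2 (Part 2 Exclusion Criteria), criterion 1, begins with the stem "Participants with known symptomatic brain metastases, with the following 2 exceptions". Exception (a) deals with metastases already diagnosed and treated. Exception (b) deals with those found at screening: "Participants with newly diagnosed brain metastases identified by a screening brain MRI who are clinically asymptomatic are eligible if" the investigator finds the clinical status acceptable and all other criteria are satisfied, "including being neurologically stable for 3 months since the screening brain MRI".

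The timing of screening is set in several places:

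- Part 2 Schedule of Activities, footnote 1 (Screening): "To be obtained within 28 days prior to study entry".
- Section 3.1.2, on the active treatment period: "This includes a 28 day screening period followed by 2 cycles of vaccine treatment".
- Part 2 Schedule of Activities, footnote 23 (Tumor Assessments), repeated in section 7.4: "Screening images may be obtained within 5 weeks of registration".
- Appendix 3 (RECIST), on an adequate baseline: "all required scans must be done within 28 days prior to treatment".

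Footnote 23 also covers brain imaging: "Baseline central nervous system (CNS) imaging MRI or CT Brain to be conducted only if clinically indicated". It gives the brain scan no separate or longer window.

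**The concern.** The 3-month clock in exception (b) starts at the screening scan, yet a scan counts as a screening scan only if it is recent. A participant cannot be within the screening window and also three months past the MRI that opened it. The exception appears to admit a group and then sets a condition that this group cannot satisfy on the documented timetable.

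The stem adds a second conflict. It excludes people with symptomatic metastases, while exception (b) is written for people without symptoms. Someone the stem does not exclude needs no exception, so it is unclear whether the conditions in (b) bind at all.

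At stake is who may be enrolled and dosed in Part 2. An eligibility rule about brain metastases should give the same answer to everyone who reads it, and this one does not.

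**Working it through.** The check is day arithmetic followed by a reading of the stem against the exception. The plan states no figure of its own to reproduce.

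**Time required from the screening MRI to entry**

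- On the 28-day month that the Part 2 maintenance schedule defines (used here as the shortest reading): 3 × 28 = 84 days.
- In calendar months: 89 to 92 days, depending on the months spanned.

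**Time available from the screening MRI to entry**

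- Screening window (Schedule of Activities footnote 1; section 3.1.2): 28 days.
- Widest image window (footnote 23; section 7.4): 5 × 7 = 35 days before registration. The allowance for standard-of-care scans in the same footnote, 28 days with a 7-day tolerance, is no wider: 28 + 7 = 35. The schedule places registration on Cycle 1 Day 1, so it leaves no further waiting time between registration and entry.
- Appendix 3: 28 days before treatment.

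**Shortfall = required − available**

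| Reading of 3 months | 28-day window | 35-day window |
|---|---|---|
| 84 days | 84 − 28 = 56 | 84 − 35 = 49 |
| 89 days | 89 − 28 = 61 | 89 − 35 = 54 |
| 92 days | 92 − 28 = 64 | 92 − 35 = 57 |

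The smallest shortfall under any combination is 49 days. Footnote 2 of the schedule lets consent be taken more than 28 days before entry, but that does not lengthen the window for screening procedures.

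**Can a participant wait and return?** The only re-screening provision found is in Appendix 7 and concerns a resolved infection. A participant who waited three months would then arguably have previously diagnosed metastases and fall under exception (a), which has different conditions, including completed treatment.

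**Stem against exception.** Take an asymptomatic participant with metastases first seen on the screening MRI.

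1. If the stem governs, the metastases are not symptomatic, criterion 1 is not triggered, and the participant is not excluded by it.
2. If exception (b) governs, the 3-month condition applies, it cannot be met in one screening attempt, and the participant is excluded.

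Both follow from the words as they stand, and they are opposite.

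**The case against.** The strongest case on the other side accepts the timing conflict and disputes its consequences. Most of that case stands.

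- **The group may be very small.** Section 7.4 says baseline brain imaging is not required except to rule out metastases in symptomatic participants, and footnote 23 and exception (b) limit it to clinical indication. Exception (b) needs someone who is asymptomatic and was scanned anyway. This stands: the documents give no count, and it could be zero.
- **Enrolment is checked centrally.** A reader might infer that sites will enrol different populations. Section 5.1 requires the sponsor's written confirmation of enrolment and permission to dose for each participant, so divergence between sites is possible but not shown.
- **No analysis set is shown to be affected.** A reader might infer damage to the per-protocol set. Section 9.1 defines that set by major deviations in the 28 days after first vaccination, and section 9.5 uses it for the main dose-limiting toxicity analysis, which concerns the Part 1 primary endpoint. Section 9.4 rests efficacy on mITT and EP, and mITT depends on receiving the Cycle 1 Day 1 components.
- **Enrolment need not be a breach.** Under the stem reading, enrolling such a participant breaches nothing. That is correct, and it is part of the problem: the text does not settle which reading applies.
- **Re-screening is not forbidden.** This is also correct, so the condition fails within one screening attempt rather than in every conceivable sequence. But the protocol describes no such route for this group.

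None of these points removes the contradiction between the 3-month condition and the windows, or between the stem and the exception.

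**Conclusion.** The criterion is wrong as written and should be corrected. The condition in exception (b) needs 84 to 92 days after the screening MRI, the documents allow 28 days or at most 35, and the gap is 49 to 64 days depending on which definitions are paired. Separately, the stem and the exception give opposite answers on the eligibility of asymptomatic participants.

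The result assumes one screening attempt and that the brain MRI falls under the same image window as the other baseline scans, since no other window is given. The 28-day month comes from the maintenance schedule; using it here is the reading most favourable to the plan.

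The size of the effect on enrolment cannot be stated. A reader might go further and infer bias in the clinical benefit rate, or a prognostic imbalance in the cohort; the documents support neither, because they give no number of affected participants and no outcome figures for them. Section 4.2.1 carries the same 3-month wording for Part 1, but that part is complete, so the correction matters only for Part 2.

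**What to change.** In section 4.2.2, the sponsor should reconcile three things so that eligibility of participants with screening-detected, asymptomatic brain metastases has a single reading:

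1. the stem of criterion 1, against the people exception (b) describes;
2. the reference date of the 3-month condition in exception (b);
3. the 28-day screening window and the 5-week image window, including whether either is meant to apply to the brain MRI and whether re-screening is intended for this group.

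Which of these passages changes, and in what direction, is a clinical decision for the sponsor; no rule is proposed here. The cost is wording at the next protocol amendment, with the matching schedule footnotes brought into line. It requires no change to sample size or analysis.
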